## **9. Description of the ethical aspects of the research**

The study addresses the issues of confidentiality and protection of personal data. The consent form does not contain contact information, confidential information, date of birth or ID code. Sensitive personal data is processed in accordance with the procedure established in the University Hospital of Tartu, which is in accordance with the requirements provided for in the Personal Data Protection Act.

Personal data is collected and then coded. The coded data is further processed and analyzed. Personal data is stored in a folder on the University of Tartu OneDrive server, which is accessible to the investigators. The link between the data collected during the study and the patient's identity is known only to the researcher conducting the interview and the researchers who have access to the code key. The code key will involve the following information: the patient's name, study ID, personal identification code, phone number, and the date of data collection. The code key will be deleted one year after the follow-up check is completed. After that, the data will become anonymous. The data will be anonymized by 04/2026. Anonymous data will be stored in a OneDrive folder protected by a password at the University of Tartu. Pseudonymized data (i.e., the study data before code key is deleted) can only be accessed by the researchers involved in the study. Copies of the consent forms

are stored in a locked office at the University of Tartu Hospital, in a locked cabinet. The locked office and cabinet are located on the sixth floor of the University of Tartu Hospital's L-building, room L6027. Informed consent forms will be kept until 06/2032. The responsible data controller is the University of Tartu.

#### **10. Information about previous or similar projects undertaken elsewhere**

The researchers have been a part of a similar project conducted at Tartu University Hospital from December 2023 to May 2024. The aim of the project was to establish whether a limb circumference, namely calf circumference (CC) or mid-upper arm circumference (MUAC), has the potential to become the preferred muscle mass assessment method of a standardised, globally accessible GLIM protocol. In both males and females there was good correlation between CC and fat-free mass index (FFMI) in patients without obesity. The correlation between CC and FFMI was weaker in patients with obesity and almost absent in females with obesity. The researchers have not encountered any problems. This experience helps to improve confidence in the feasibility of the new study given a similar time frame.

After we complete the current study, we also aim to look at this previous dataset to find out whether the new corrections work for the patients with obesity. This will validate the results of the study.

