## **4. Brief overview of previous research on the same topic**

Muscle mass is a common criterion for the assessment of malnutrition and sarcopenia (1). However, evaluation of muscle mass with gold-standard methods is often challenging in healthcare settings due to their high cost, lack of portability, and impracticality (2). Anthropometric measurements such as calf circumference (CC) are cost-effective, simple

alternative techniques that can be performed to estimate muscle mass in clinical settings (3,4).

Earlier Asian validation studies affirmed the good diagnostic performance of CC for detecting low appendicular lean mass and sarcopenia (5,6). The Asian Working Group for Sarcopenia (AWGS) 2019 consensus recommended the addition of calf circumference in order to improve the sensitivity of sarcopenia screening (SARC-F)(7). Compared with SARC-F, Calf circumference (CC) had better diagnostic performance but its performance decreased in those with sarcopenic obesity (especially in women)(8).

The Global Leadership Initiative on Malnutrition (GLIM) also supports the use of calf circumference or mid-upper arm circumference for assessment of skeletal muscle mass when DEXA, BIA or CT are not available (3). A cohort study validated the use of GLIM criteria for malnutrition diagnosis by comparing CC and MUAC measurements against the Subjective Global Assessment (SGA) in hospitalized patients. Both measures showed strong accuracy for detecting malnutrition (9). However, CC's diagnostic performance decreases in patients with a  $BMI \geq 30 \text{ kg/m}^2$ , particularly women. In patients with obesity, study showed weaker correlations between CC and fat-free mass index (FFMI) as a measure of muscle mass (10).

This highlights the need for future research to define new strategies and threshold corrections for accurate muscle mass assessment in clinical practice for patients with obesity.

2. Fayh APT, de Sousa IM, Gonzalez MC. New insights on how and where to measure muscle mass. *Curr Opin Support Palliat Care.* 2020;14(4):316–23.

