## **5. Purpose, summary and justification of the proposed research**

The issue of obesity for calf circumference (CC) has been addressed in various studies. Calf skinfold thickness has been suggested for adjusting CC in patients with obesity, but the method has limitations, can lead to errors and it is time-consuming. The NHANES study in the U.S. showed that adjusting calf circumference for BMI helps to detect age- associated, and sex-specific lower values of calf circumference (1). However, few studies have validated BMI-adjusted CC in hospitalized patients (2).

The aim of the study is to find out whether calf circumference (CC), corrected with mid-upper arm circumference (MUAC), will provide more accurate estimate of muscle mass in patients with obesity. Mid-upper arm circumference (MUAC) is more representative of body fat mass than of muscle mass in patients with obesity, especially in women (3). Therefore, there is a reason to believe that MUAC will improve the accuracy of calf circumference as a muscle mass measure by adjusting for the influence of fat.

The research hypothesizes that calf circumference corrected with mid-upper arm circumference is more accurate than just calf circumference at detecting reduced muscle mass in patients with obesity. In case the hypothesis proves true, corrected calf circumference measurement will have the potential to be an easy and simple approach for estimating muscle mass in patients with obesity in clinical or limited settings.

3. Kurik G, et al. Poor correlation between calf circumference and muscle mass in patients with obesity. *Clin Nutr ESPEN.* 2024;63:1121.

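### The earlier Tartu dataset already showed raw CC failing in obesity and probably suggested MUAC as the corrector, so it can check the new formula but cannot independently validate the claim that corrected CC beats raw CC

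*Protocol*

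**What the plan says.** Section 10 describes "a similar project conducted at Tartu University Hospital from December 2023 to May 2024", run by the same researchers. It asked whether a limb circumference, "namely calf circumference (CC) or mid-upper arm circumference (MUAC), has the potential to become the preferred muscle mass assessment method". Its result was: "The correlation between CC and FFMI was weaker in patients with obesity and almost absent in females with obesity".

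The same section then says that, once the current study is complete, "we also aim to look at this previous dataset to find out whether the new corrections work for the patients with obesity", and concludes: "This will validate the results of the study". No other validation sample is named in the protocol.

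Section 5 states the hypothesis as a comparison: CC corrected with MUAC is more accurate than CC alone at detecting reduced muscle mass in patients with obesity. The stated reason for choosing MUAC is that "Mid-upper arm circumference (MUAC) is more representative of body fat mass than of muscle mass in patients with obesity, especially in women (3"; the citation is to reference 3 of that section, a 2024 report titled "Poor correlation between calf circumference and muscle mass in patients with obesity". Section 4 cites the same report, as its reference 10, for weaker CC–FFMI correlation in obesity.

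Section 8 says that corrected CC will be compared with DEXA in the new study and that the new cutoffs will be set there from ROC curves.

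**The concern.** A dataset can validate a comparative claim only if it did not help to form that claim. Here the comparator's poor result in the earlier data is already known. If the corrector was picked from the same data, both halves of the hypothesis (raw CC is poor, MUAC carries the fat signal) were seen there first. Any chance component of those two observations stays in the data and carries over when corrected and raw CC are compared in the same patients.

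At stake is what the study may claim. Section 5 expects that, if the hypothesis holds, corrected CC could become a simple clinical way to estimate muscle mass in obesity. Calling the method validated would encourage that use, and this is the only validation the protocol plans.

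**Working it through.** The plan gives no figure on this point, so there is nothing to reproduce. The check has two parts.

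**Tracing the sources**

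1. Section 10 states directly that raw CC performed poorly in obesity in the earlier project, and names that same dataset for the validation. No inference is needed.
2. Section 5 supports MUAC as a fat marker with one citation, the 2024 report. Section 4 cites that report for the same kind of finding that section 10 attributes to the researchers' own project. Measures, finding and timing match. That the report used this dataset is therefore probable, but it is not stated.
3. Section 8 sets the cutoffs in the new cohort, and section 10 applies the corrections afterwards. Nothing says that they are fitted to the earlier data.

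**Illustrative size (all inputs assumed)**

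The protocol gives neither the size of the earlier obese subgroup nor any correlation. The model, with standardised variables, is CC = 0.4·muscle + 0.6·fat + noise and MUAC = c·muscle + 0.6·fat + noise, where c is MUAC's true correlation with muscle. Gain = r(corrected CC, muscle) − r(raw CC, muscle).

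*Run A.* The correction is fitted by regression in 50 new patients. It is then scored in an earlier sample kept only if raw CC's r was below 0.3 and MUAC's r was below c, and in a fresh sample of the same size (8,000 replicates per setting before selection).

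| c | earlier n | gain, earlier sample | gain, fresh sample | excess |
|---|---|---|---|---|
| 0.0 | 20 | 0.089 | 0.010 | 0.079 |
| 0.0 | 40 | 0.059 | 0.008 | 0.051 |
| 0.0 | 80 | 0.043 | 0.001 | 0.042 |
| 0.2 | 20 | −0.016 | −0.023 | 0.007 |
| 0.2 | 40 | −0.015 | −0.027 | 0.012 |
| 0.2 | 80 | −0.018 | −0.023 | 0.005 |
| 0.4 | 20 | 0.043 | 0.039 | 0.004 |
| 0.4 | 40 | 0.053 | 0.042 | 0.011 |
| 0.4 | 80 | 0.057 | 0.038 | 0.019 |

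With c = 0, a positive gain appeared in about 86–87% of selected samples against 57–60% of fresh ones. Without selection (n = 40, c = 0.2) there was no excess: −0.024 against −0.025.

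*Run B.* The formula is fixed at its best weights. For c = 0 the CC–MUAC correlation is 0.4×0 + 0.6×0.6 = 0.36. The weights are then 0.4/(1 − 0.36²) = 0.460 for CC and −0.36×0.460 = −0.165 for MUAC. Samples are kept if raw CC's r lies within ±0.15, to mimic an almost absent correlation (60,000 replicates before selection).

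| c | excess gain, n = 20 / 30 / 60, selected on CC | excess gain, also selected on MUAC's r below c |
|---|---|---|
| 0.0 | 0.034 / 0.034 / 0.030 | 0.074 / 0.062 / 0.043 |
| 0.1 | 0.007 / 0.006 / 0.006 | 0.025 / 0.019 / 0.012 |
| 0.2 | 0.001 / 0.001 / 0.001 | −0.006 / −0.004 / −0.002 |

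The reason the excess is small shows at n = 30, c = 0, selecting on CC only. Raw r falls from 0.39 to 0.07, but corrected r falls with it, from 0.42 to 0.13. The gain moves only from 0.028 to 0.062.

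**The case against.** The strongest defence is that the formula and cutoffs come from new patients and meet the earlier data only afterwards. That is a genuine out-of-sample test from a different period, and it can fail. This stands. A reader might infer that the earlier dataset cannot fail, or that almost any correction would look better there. The documents support neither, and in Run A with c = 0.2 the correction did worse than raw CC on average even in the selected samples.

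A reader might also size the problem from the upper 95% limit for a true correlation when r = 0 is observed, tanh(1.96/√(n − 3)): 0.44, 0.36 and 0.25 for assumed n of 20, 30 and 60. That limit describes raw CC alone. Corrected CC is built from the same CC values in the same patients, so a chance-low raw r lowers both, and the limit is not a possible chance gain.

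Further points for the plan: section 4 cites separate work in which CC performed worse in sarcopenic obesity, especially in women, so poor raw CC is not known from this dataset alone. No text says the dataset was chosen because raw CC did badly there. Section 10 reports no MUAC–fat result, so the MUAC link is an inference. The protocol does not claim external validation, and sharing a hospital and team is not itself a fault.

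It can also be said that section 10 asks only whether the corrections work, not whether they beat raw CC. But its next sentence covers the results of the study without limit, and the study's hypothesis is that comparison. The known result of the comparator is enough to keep the point, whatever the source of MUAC.

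**Conclusion.** The point holds in a limited form, as a cheap improvement. The earlier dataset can test whether a locked formula and locked cutoffs carry over to other patients. It is not independent evidence that corrected CC is better than raw CC, because the comparator's poor result there is already known and the corrector was probably chosen from the same data. The unqualified validation sentence therefore claims too much.

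The size cannot be computed from the documents. Under the assumed inputs, the excess gain was about 0.04–0.08 when MUAC was a pure fat marker and both measures had been selected as poor, about 0.03 when only CC had been, and about 0.02 or less, or nil, once MUAC had a true correlation with muscle of 0.2 or more. The tilt is thus largest where the protocol's own premise about MUAC is most nearly true. The conclusion on MUAC rests on the shared citation; the conclusion on the known comparator does not.

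**What to change.** In section 10, replace the validation sentence with a statement that the earlier dataset helped to form the hypothesis and serves as a secondary consistency check. Add that:

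- the correction formula and cutoffs are locked from the new cohort before they are applied to the earlier data;
- sensitivity and specificity of corrected CC at those cutoffs are reported there;
- the claim that corrected CC is more accurate than raw CC rests on the new cohort;
- the protocol states whether the 2024 report cited in sections 4 and 5 used this dataset;
- validation in data not used to form the hypothesis is still needed.

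The cost is a few sentences and a fixed order of analysis, with no added patients or measurements. The downside is a final claim weaker than *validated*. If the report turns out to rest on other data, the MUAC part can be softened, but the limit on the comparison with raw CC should stay.

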#### **11. Supplementary papers:**

##### **11.1 CVs of the Researchers**

##### **11.2 Information and consent form(s + Russian)**
